## 5.6 Overview of potential benefits and, where applicable, of predictable and known risks for the patients participating in the research project

---

By comparing two strategies for nutritional support initiation, this study will strive to standardize the initiation of nutritional support in patients treated with mechanical ventilation and one or more vasoactive amines. At the acute phase of their ICU management, the study patients will receive a single nutritional modality, i.e., either parenteral nutrition (early parenteral group, P group) or enteral nutrition (early enteral group, E group) for at least 72 h and no longer than 7 days. Each of these two modalities will be used according to a pre-defined protocol that will include an estimate of energy needs based on body weight. Beyond the first study week, the ICU teams will give preference to the enteral route, except in patients with acute bowel disease constituting an absolute contraindication to enteral nutrition. Thus, parenteral and enteral intakes will be combined according to each patient's needs.

The standardization of nutritional support will constitute in itself a source of benefits to the study patients (15). This study generates no additional risks to the patients. Nutritional support, whether delivered enterally or parenterally, is among the first-line treatments used routinely in the ICU. Raising healthcare worker awareness about good clinical practice in the area of nutritional support receives careful attention as a matter of course in ICUs. Finally, to date, no study has produced definitive information on the risks and benefits of enteral versus parenteral nutrition.

Similarly, the ancillary studies will pose no additional risks to the patients. More specifically, they will require no additional biological-sample collections. The citrulline and I-FABP assays in Ancillary Study 1 will be performed on a fraction of the blood samples drawn for the routine management of critically ill patients. These blood samples will simply need to be increased slightly (by about 2 mL). The pepsin and salivary amylase assays needed for Ancillary Study 2 will be performed on tracheal aspirates obtained as part of the standard care of patients receiving mechanical ventilation. Thus, no additional procedures are required.

## 5.7 Statement that the research project will be conducted in compliance with the study protocol and with good clinical practice guidelines

The investigator undertakes to ensure that this research is conducted

- in compliance with the study protocol and
- in compliance with current French and international good clinical practice guidelines.

## 5.8 Description of the study population

---

This study will include adults admitted to the ICU and eligible for enteral or parenteral nutrition within 24 h after endotracheal intubation (or within 24 h after ICU admission if intubation occurred before ICU admission), for a predicted duration of at least 2 days. Furthermore, eligibility for study inclusion will require a serious critical illness defined as a need for vasoactive amine therapy to treat shock combined with invasive mechanical ventilation started within the past 24 h. The controlled nutritional-support strategy will be used only during the acute phase of intensive care, defined as the first 7 days in the ICU. Section 5 describes the inclusion and exclusion criteria used to select the study patients.

### 3) STUDY OBJECTIVES

#### 5.9 Primary objective

The primary objective of this research project is to assess the hypothesis that a strategy involving first-line early enteral nutrition decreases day-28 all-cause mortality in mechanically ventilated patients receiving vasoactive amine therapy for shock, compared to a strategy involving first-line early parenteral nutrition.

#### 5.10 Secondary objectives

The secondary objectives consist in comparing the following variables in the two groups:

- Nosocomial infections:
  - VAP: proportion of patients with at least one VAP episode, VAP incidence density, number of VAP episodes
  - Bacteremia: proportion of patients with at least one episode of bacteremia, incidence density of bacteremia
  - Central venous catheter (CVC)-related infections: proportion of patients with at least one CVC-related infection, incidence density of CVC-related infections
  - Urinary tract infections: proportion of patients with at least one urinary tract infection, incidence density of urinary tract infections
  - Soft tissue infections: proportion of patients with at least one soft tissue infection, incidence density of soft tissue infections
- Descriptive bacteriological data (organisms recovered and antibiotic resistance profile for each nosocomial infection)
- Proportion of patients with at least one episode of vomiting or regurgitation
- Proportion of patients with at least one episode of diarrhea
- Proportion of patients with at least one episode of constipation
- Proportion of patients with at least one episode of documented bowel ischemia
- Number of calories delivered enterally and parenterally each day
- Volume of enteral and parenteral feed delivered each day
- Ratio of prescribed over delivered calories
- ICU mortality, day-90 mortality, and hospital mortality

---

- Changes in nutritional markers during follow-up (measured at the end of mechanical ventilation, on day 7 in patients on mechanical ventilation for more than 7 days, and at ICU discharge)
- Proportion of patients with at least one episode of liver dysfunction (liver function will be evaluated at the end of mechanical ventilation, on day 7 in patients on mechanical ventilation for more than 7 days, and at ICU discharge)
- ICU stay length
- Hospital stay length
- Total time on mechanical ventilation
- Body weight changes from ICU admission to day 7 and from ICU admission to ICU discharge

## 5.11 Objectives of the ancillary studies

- Ancillary study 1
  - Primary objective: To demonstrate that a strategy involving early first-line enteral nutrition is associated with improved preservation of gut mucosal integrity, as assessed based on the plasma citrulline level at H72, compared to a strategy involving early first-line parenteral nutrition
  - Secondary objectives: To compare the effects of enteral and parenteral nutrition on the course of organ failures, bacteremia, gastrointestinal intolerance, bowel transit time, and plasma citrulline and I-FABP levels
- Ancillary study 2
  - Primary objective: To evaluate the impact of enteral nutrition on microaspiration of gastric content
  - Secondary objective: To evaluate the impact of enteral nutrition on microaspiration of pharyngeal secretions

## 5.12 Impact

If the study hypothesis is confirmed, then early enteral nutrition will become the reference standard method of nutritional support in mechanically ventilated patients with

---

shock, based on improvements in morbidity and mortality rates and in the overall outcome of patients at the acute phase of ICU management.

The ancillary studies will clarify the impact on gut function of the route of administration of nutritional support, as well as the pathophysiology of gastric-content aspiration, in patients receiving mechanical ventilation.

## 4) STUDY CONCEPTS

### 5.13 Detailed descriptions of the primary endpoint and, where applicable, of the secondary endpoints

#### 4.1.1 Primary endpoint

The primary endpoint is all-cause mortality by day 28 (D28). Information on this endpoint will be collected on the 28th day after inclusion of the patient in the study. For patients who have been discharged, information on the primary endpoint will be collected by a telephone call to the patient at home.

- Proportion of patients with at least one episode of diarrhea defined as liquid stools in a volume greater than 300 mL/24 hours in patients with a fecal collector or as more than four loose stools/24 hours (15).
- Proportion of patients with at least one documented episode of bowel ischemia defined as absent blood flow in one of the main arteries supplying the bowel (superior mesenteric artery, inferior mesenteric artery, or celiac artery) with evidence of bowel wall compromise on an imaging study (computed tomography angiography [CTA], angiography, or magnetic resonance angiography [MRA]) or presence of criteria for colonic ischemia according to the Favier classification system (stage I, petechiae; stage II, petechiae and superficial ulcers; and stage III, necrotic ulcers and polypoid lesions) by endoscopy (rectosigmoidoscopy or colonoscopy) (70)
- Number of calories (in Kcal) delivered enterally and parenterally:
  - daily mean during the first week
  - daily mean throughout the time on mechanical ventilation
- Ratio (as a %) of prescribed over delivered calories delivered enterally and parenterally:
  - daily mean during the first week
  - daily mean throughout the time on mechanical ventilation
  - proportion of patients who achieved their calorie target on each follow-up day
- Volume of liquid feed (in mL) delivered
  - daily mean during the first week
  - daily mean throughout the time on mechanical ventilation

- ICU mortality, 90-day mortality, and hospital mortality; to confirm deaths by day 90, we will search the epidemiological causes-of-death database (CépiDc, *Centre d'épidémiologie sur les causes médicales de décès*).
- Mean changes in serum albumin, prealbumin, transthyretin, and C-reactive protein (CRP) measured at baseline, at the end of mechanical ventilation, on day 7 (in patients on mechanical ventilation for more than 7 days), and at ICU discharge
- Proportion of patients with at least one episode of liver dysfunction during follow-up; liver function will be evaluated at the end of mechanical ventilation, on day 7 (in patients on mechanical ventilation for more than 7 days), and at ICU discharge; liver dysfunction will be defined as serum bilirubin  $>50 \mu\text{mol/L}$  and/or elevation  $>3\text{N}$  in one or more liver enzymes ( $\gamma$ -glutamyltransferase, alkaline phosphatase, and ASAT-ALAT).
- ICU stay length
- Hospital stay length
- Time on mechanical ventilation
- Changes in mean body weight determined at baseline, on day 7, and at ICU discharge

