In addition, the safety of enteral nutrition in patients with circulatory failure, particularly those with low splanchnic blood flow, remains in doubt. In healthy individuals, enteral nutrition increases blood flow in the superior mesenteric artery by over 50%. As a result, in patients with circulatory failure, enteral nutrition may induce nonocclusive mesenteric ischemia, a condition associated with mortality rates of 70% to 100%. Although these potential complications have not been convincingly linked to enteral nutrition, they lead many physicians to delay the initiation of nutritional support by several days or to prefer parenteral nutrition at the acute phase of the management of critically ill patients and/or of patients with shock. This attitude is strengthened by the absence of a vast multicenter randomized trial evaluating the impact of early enteral nutrition on outcomes of patients receiving mechanical ventilation. Current recommendations are based on observational or retrospective data and on studies that have inadequate statistical power. Thus, several recent editorials have emphasized the need for well-designed clinical trials capable of resolving current uncertainties about the nutritional management of mechanically ventilated patients. A recent randomized controlled trial found that parenteral nutrition added to inadequate enteral nutrition was associated with longer stays and higher infection rates while failing to affect mortality when started early instead of at the end of the first week in the ICU. An as yet unpublished study from Switzerland investigated the same topic and found contrary results. These studies fail to establish that the enteral route is superior over the parenteral route at the acute phase. Choosing between these two routes is among the crucial unresolved issues in the management of mechanically ventilated patients in the ICU. The working hypothesis for the present study is that, compared to early parenteral nutrition, early enteral nutrition is associated with lower mortality rates in patients receiving invasive mechanical ventilation and vasoactive agents for shock.

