The lower intestinal tract can also be the site of complications characterized by ischemia despite patency of the blood vessels, a condition known as nonocclusive mesenteric ischemia (NOMI) (55). NOMI may affect 20% to 30% of ICU patients with severe circulatory failure. Intense splanchnic vasoconstriction designed to preserve blood flow to essential organs (the brain, heart, and kidneys) can result in necrotizing enterocolitis, a condition that is fatal in 70% to 100% of cases (56, 57). The main causative factors are medications (catecholamines, vasoconstrictors, cardiovascular drugs), patient characteristics (chronic hemodialysis, heart surgery, multiple trauma), and critical complications (acute respiratory distress syndrome, septic shock, cardiogenic shock, fluid and sodium overload) (58-60). The potential role for enteral nutrition in the development of NOMI remains controversial. A study involving superior mesenteric artery blood-flow measurement 3 h after the introduction of nutritional support in volunteer ICU patients failed to conclusively resolve this issue (61). Enteral nutrition was associated with a greater than 50% blood-flow increase and parenteral nutrition with a greater than 60% decrease, indicating a theoretical risk of a mismatch between oxygen supply and demand in the splanchnic territory in patients with acute circulatory failure receiving enteral nutrition.

Another contributor to the current underuse of early enteral nutrition in many patients is the conflicting nature of findings from available studies. In addition, no study to date has demonstrated that a specific nutritional modality is associated with decreased mortality.

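### The bowel-ischemia endpoint does not count nonocclusive ischemia seen on imaging with patent main arteries, so it can understate any absolute excess of the bowel hazard that the protocol itself names

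*Combined protocol and SAP*

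**What the plan says.** Section 4.1.2 (Secondary endpoint) gives two routes to an event.

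- **Imaging.** A "documented episode of bowel ischemia defined as absent blood flow in one of the main arteries supplying the bowel" (superior mesenteric, inferior mesenteric or celiac), together with evidence of bowel-wall compromise on CT angiography, angiography or MR angiography.
- **Endoscopy.** "or presence of criteria for colonic ischemia according to the Favier classification system", stages I to III, at rectosigmoidoscopy or colonoscopy. On the natural reading this stands alone, without an arterial condition, although the sentence does not say so outright.

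Nothing else widens the definition. Section 5.10 (Secondary objectives) says only "Proportion of patients with at least one episode of documented bowel ischemia", the Synopsis lists do the same, and section 7.1.4 gives only the analysis method, which is that of the primary endpoint (chi-square test, section 7.1.3).

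On the hazard, section 5.5 (Overview of the research project) describes complications of the lower intestinal tract "characterized by ischemia despite patency of the blood vessels, a condition known as nonocclusive mesenteric ischemia (NOMI". The Synopsis says that in circulatory failure "enteral nutrition may induce nonocclusive mesenteric ischemia, a condition associated with mortality rates of 70% to 100" percent, and adds that "these potential complications have not been convincingly linked to enteral nutrition". Section 5.5 likewise says: "The potential role for enteral nutrition in the development of NOMI remains controversial".

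The trial is open, and section 4.3.2 plans adjudication for nosocomial infections only.

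**The concern.** The imaging route requires the arterial finding that the protocol's own description of NOMI rules out. A patient with ischemic small bowel on CT angiography and flow in all three main arteries fits that description, yet is scored as having no bowel ischemia. So is a patient whose ischemia is shown only at laparotomy, on histology or at autopsy.

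This is the main trial's only endpoint for the incidence of bowel ischemia. Ancillary study 1 measures I-FABP in 170 patients, but that is an indirect marker of enterocyte damage. If enteral feeding does add NOMI, part of the excess goes uncounted, and a null result could be taken as reassurance on a hazard that the endpoint saw only in part. That matters because section 5.12 (Impact) expects a positive trial to make early enteral nutrition the reference standard in ventilated patients with shock.

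**Working it through.** **1. What the definition counts.** Setting section 4.1.2 beside section 5.5:

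| Presentation | Counted? |
|---|---|
| Absent main-artery flow with bowel-wall compromise on imaging | Yes |
| Colonic ischemia (Favier stage I–III) at endoscopy, arteries patent | Yes, on the natural reading |
| Bowel-wall ischemia on imaging, main arteries patent, no qualifying endoscopy | No |
| Ischemia shown only at surgery, histology or autopsy | No |

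The exclusion of patent-artery NOMI is complete on the imaging route and partial for the endpoint as a whole.

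**2. The plan's own figure.** Section 7.2 gives 37% versus 32%, alpha 4.9%, power 80% and 1427 per group. With pooled variance under the null, two-sided alpha and no continuity correction:

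n = [z(α/2)·√(2p̄(1−p̄)) + z(β)·√(p₁(1−p₁)+p₂(1−p₂))]² / (p₁−p₂)²

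With p̄ = 0.345, z(α/2) = 1.9686 and z(β) = 0.8416, n = 1426.5, which rounds up to 1427. This reproduces the stated figure, so the same test and alpha are used below.

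**3. Model for the endpoint.** The documents give no rate, effect or power for it. Let o be the risk of counted occlusive ischemia, equal in both arms; N the NOMI risk in the parenteral arm; R the true NOMI risk ratio (enteral over parenteral); and s the share of NOMI that the definition counts, the same in both arms.

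- Observed parenteral risk: P = o + sN
- Observed enteral risk: E = o + sNR
- Observed risk difference: sN(R−1), that is, s times the true excess
- Observed RR − 1 = (R−1) × sN/(o + sN)

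The last line shows what moves the ratio. It is pulled toward 1 by the factor sN/(o + sN), the NOMI share of the parenteral events counted. The ratio barely moves while NOMI dominates the count, and it falls as occlusive events become a substantial share.

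**4. Inputs.** n = 1427 per arm and two-sided alpha 0.049. Assumed: o = 0.5%, with s and R as shown. The upper-bound N of 20% is the lower end of the 20% to 30% that section 5.5 gives for patients with severe circulatory failure. The low N of 2% is an assumption.

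Power = Φ{[|E−P|√n − 1.9686·√(2p̄(1−p̄))] / √(P(1−P)+E(1−E))}, with p̄ = (P+E)/2. For 20.5% versus 25.5%: (0.05 × 37.776 − 1.1716)/0.5941 = 1.207, so power is 89%.

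| NOMI, enteral vs parenteral | s | E vs P | Difference (points) | RR | Power |
|---|---|---|---|---|---|
| 25% vs 20% | 1 | 25.5% vs 20.5% | 5.0 | 1.24 | 89% |
| | 0.3 | 8.0% vs 6.5% | 1.5 | 1.23 | 34% |
| | 0.1 | 3.0% vs 2.5% | 0.5 | 1.20 | about 12% |
| | 0 | 0.5% vs 0.5% | 0 | 1.00 | none (alpha only) |
| 4% vs 2% | 1 | 4.5% vs 2.5% | 2.0 | 1.80 | 83% |
| | 0.3 | 1.7% vs 1.1% | 0.6 | 1.55 | 27% |
| | 0.1 | 0.9% vs 0.7% | 0.2 | 1.29 | about 9% |
| | 0 | 0.5% vs 0.5% | 0 | 1.00 | none (alpha only) |

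At s = 0.3, occlusive events are 0.5/6.5 = 8% of the parenteral count in the first scenario and 0.5/1.1 = 45% in the second. That is why the ratio is nearly unchanged in one and clearly reduced in the other.

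**5. Unequal work-up.** Suppose feeding route has no effect, NOMI is 2% in both arms, and more endoscopy in the enteral arm makes s 0.5 there against 0.3 in the parenteral arm. The observed risks are 0.5 + 0.5 × 2 = 1.5% and 0.5 + 0.3 × 2 = 1.1%, a ratio of 1.36 with no true difference. The direction of error is therefore not fixed.

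**The case against.** The strongest reply is that section 4.1.2 is a defensible, specific definition. The endpoint is called bowel ischemia, not NOMI. Section 5.5 is background, and no section says that the endpoint measures NOMI or that a null result would clear enteral feeding of it. An objective arterial criterion also has merit in an open trial. This stands in part: the fault is a mismatch between the endpoint and the hazard that motivates it, not two rules that contradict each other.

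Three stronger readings are tempting, and the documents do not support them.

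- **That NOMI is wholly or largely excluded.** The endoscopic route has no patency condition and accepts even stage I petechiae, so it can count colonic NOMI. The documents give neither the colonic share of NOMI nor the frequency of endoscopy, so the share missed cannot be stated.
- **That the risk ratio must be pulled strongly toward 1 because missed cases pile up in the enteral arm.** Nothing in the definition makes capture of NOMI differ by arm. With one capture share, missed cases follow the NOMI risks themselves: at s = 0.3 and 25% versus 20%, 17.5% against 14.0% of patients, a ratio of 1.25. At the only frequency that the documents give, the observed ratio hardly changes.
- **That the error always favors no difference.** Step 5 of the working shows that unequal work-up can reverse it.

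It is also fair to say that dropping the arterial criterion costs specificity, so a wider definition needs masked review.

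**Conclusion.** The definition does not count NOMI seen on imaging with patent main arteries, notably in the small bowel, or ischemia shown only at surgery, histology or autopsy. Confidence in this is high, because it follows from the text. If enteral feeding adds NOMI and work-up is equal, the endpoint reports s times the true absolute excess and loses power: from 89% to 34%, or from 83% to 27%, at an assumed 30% capture. Material attenuation of the ratio is conditional on case mix, and confidence in its size and direction is low. These figures rest on an assumed 0.5% occlusive risk, assumed NOMI effects and an equal capture share. The 20% rate, which the protocol states for severe circulatory failure, serves only as an upper bound.

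A null result on this endpoint would not by itself exclude an effect on NOMI. The primary endpoint is unaffected, and deaths from NOMI still count in day-28 all-cause mortality. Severity is minor to moderate, as this is a secondary safety endpoint.

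**What to change.** Align the section 4.1.2 endpoint with the hazard described in the Synopsis and section 5.5.

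1. Count bowel-wall ischemia or necrosis documented by imaging, endoscopy, surgery, histology or autopsy done for clinical reasons, irrespective of main-artery patency. List the qualifying bowel-wall imaging findings in advance.
2. State that the endoscopic criterion stands alone.
3. Record the basis of diagnosis and main-artery patency (patent / absent flow / not assessed).
4. Report by arm all bowel ischemia, the occlusive and nonocclusive subsets, and the current definition as a sensitivity analysis.
5. Have the adjudication committee already planned in section 4.3.2 review reported cases, with feeding route masked where the records allow. If that workload is judged too large, state that the endpoint is unadjudicated and that a null result does not exclude an effect on NOMI.

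**Cost.** The rewording and a short case-report-form item are cheap and need no new procedure or patients. The form is not in the documents, so it may already hold the item; section 4.6 mentions only an abdominal complication among the reasons for reducing or stopping feeding. Adjudication workload is uncertain. At full capture the two scenarios imply 1427 × (0.045 + 0.025) ≈ 100 and 1427 × (0.255 + 0.205) ≈ 656 true cases, plus suspected cases later rejected. The downside is some loss of specificity, which the sensitivity analysis would show.

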##### a. General principles

Nutritional support will be started as soon as possible after the initiation of invasive mechanical ventilation and no later than 24 hours after intubation or after ICU admission in patients intubated before ICU admission.

The calorie target for each patient will be estimated based on body weight as 20-25 Kcal/Kg/day during the acute phase (7 days at the most) then 25-30 Kcal/Kg/day from day 7 to extubation. In obese patients (BMI > 30 Kg/m^2), the body weight yielding a BMI of 30 will be used to estimate the calorie target.

Nutritional support will be prescribed as a flow rate (mL/hour) and started at the prescribed flow rate (as opposed to increased gradually). The feed will be delivered continuously, over the 24-hour cycle, with no interruptions. Actual feed delivery will be monitored regularly based on the volumes delivered relative to the predefined daily calorie targets. In addition, special attention will be directed to avoiding delays. Any interruption in feed delivery will be reported to the ICU physician in charge. Except in special situations, nutritional support will not be interrupted while transporting the patient. However, when enteral or parenteral nutrition must be interrupted (e.g., for a specific gastrointestinal or radiological investigation), the flow rate will not be increased to compensate for the interruption. Finally, the patient will be in the semi-recumbent supine position with the torso at 30° to 45° from the horizontal plane.

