#### Demographics and clinical data

- At inclusion: date of birth, sex, date of ICU admission, reason for ICU admission, McCabe and Knaus scores, chronic co-morbidities, body weight, height, BMI, and SOFA score
- at H24: SAPS II and SOFA score

---

- follow-up: date of final extubation, date of ICU discharge, date of hospital discharge (Acute care hospital), vital status at ICU discharge, and vital status at hospital discharge

Nutritional data, every day, *until extubation of the patient*: name of the enteral or parenteral preparation; target number of calories; volume and calories delivered each day; vomiting (yes/no every 4 hours, with the time of any vomiting episodes); decrease or discontinuation of nutritional support (yes/no); reason for decreasing or discontinuing nutritional support (vomiting, diarrhea, acute pseudoobstruction of the colon, other acute abdominal symptoms, abdominal complication, imaging study/other); presence, volume, and appearance of the stools (yes/no every 4 hours, exact volume in mL and, where applicable, qualitative description as normal/liquid/mucopurulent/mucous/bloody); and diarrhea with its presumed cause (intolerance to nutritional support, medication, *Clostridium difficile*, other).

Treatments given: Every day, *until extubation of the patient*: prokinetic agent (dose/24 h), polyethylene-glycol (dose/24 h), neostigmine (dose/24 h), sedation (dose/24 h and nature of the hypnotic and/or opioid agents), neuromuscular blockers (dose /24 h), catecholamines (dobutamine, noradrenaline, or adrenaline; yes/no regardless of duration and dose), renal replacement therapy (yes/no), antibiotics (yes/no), insulin (total dose/24 h), volume of IV fluids (total/24 h), and gastric anti-secretory agents (sucralfate, proton-pump inhibitors, histamine receptor antagonists, other).

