- The number of calories delivered each day by the enteral and parenteral routes: changes over time in delivered calories will be represented graphically by boxplots created each day on the same graph; changes over time will be compared between the two groups using a mixed linear model, after data transformation if necessary
- Volume of enteral and parenteral feeds delivered each day: the analysis method will be the same as for the number of calories
- Ratio of prescribed over delivered calories: the proportions of patients who achieved their daily calorie target will be determined at each follow-up time point (in days) and will be compared between the two groups using a logistic random effects model
- ICU mortality, 90-day mortality, and hospital mortality: day-90 mortality will be analyzed in the same way as day-28 mortality; for ICU and hospital mortality rates, competing-risk models will be used, as ICU discharge and hospital discharge compete with death during the stay
- Nutritional markers and body weight: changes over time in nutritional markers and body weight will be analyzed using the method described above for the number of calories delivered
- Proportion of patients with at least one episode of liver dysfunction: the method will be the same as for the primary objective
- Times in the ICU, in the hospital, and on mechanical ventilation will be compared between the two groups using nonparametric Wilcoxon tests

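### Calories are prescribed per kg but compared in raw Kcal with no weight term: some precision is lost, and the Kcal mean alone cannot be read against the per-kg target

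*Combined protocol and SAP*

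**What the plan says.** **Prescription.** Section 4.2.3 a: "The calorie target for each patient will be estimated based on body weight as 20-25 Kcal/Kg/day during the acute phase", rising to 25-30 Kcal/Kg/day afterwards. For a BMI above 30, "the body weight yielding a BMI of 30 will be used to estimate the calorie target". Section 6.1 gives both arms the same acute-phase target.

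**Endpoint.** Section 4.1.2 lists "Number of calories (in Kcal) delivered enterally and parenterally", as a daily mean over the first week and over the whole time on ventilation. Neither the objectives, the endpoints nor the analysis section lists a Kcal/kg summary.

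**Analysis.** Section 7.1.4: "changes over time will be compared between the two groups using a mixed linear model, after data transformation if necessary". No weight term is named, and the random-effects structure is not given.

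**Companion endpoints.** Section 4.1.2 also lists "Ratio (as a %) of prescribed over delivered calories delivered enterally and parenterally" and the "proportion of patients who achieved their calorie target on each follow-up day". Section 7.1.4 assigns the second a logistic random effects model.

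**Data.** Section 4.6 records "chronic co-morbidities, body weight, height, BMI, and SOFA score" at inclusion, and each day until extubation the calorie target and the calories delivered.

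**The concern.** Two patients fed exactly as prescribed can differ widely in Kcal because one is larger. That spread says nothing about how well feeding was delivered, yet it enters the standard error of the comparison in Kcal.

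There is also a question of reading the result. The trial compares routes at a common calorie target. A reader who wants to know whether the arms received similar doses would look for intake on the scale of the prescription, and a mean in Kcal does not give it directly. At stake are the precision and the legibility of a secondary process measure, not the mortality result.

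**Working it through.** **1. The plan's own figure.** No sample size is stated for calories; 1427 per group is powered on day-28 mortality (section 7.2). It serves here only as the number available. With 37% v 32%, alpha 4.9% taken as two-sided, 80% power and pooled variance under the null:

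n = [1.969 × √(2 × 0.345 × 0.655) + 0.842 × √(0.37 × 0.63 + 0.32 × 0.68)]² / 0.05² = 1427, which matches.

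**2. What the per-kg rule implies in Kcal.** A target of 20-25 Kcal/Kg/day is 1000-1250 Kcal at 50 kg, 1500-1875 at 75 kg and 2000-2500 at 100 kg (the last if BMI is 30 or less). These ranges do not overlap, although all three patients are on target.

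**3. Assumptions, since the documents give no SDs.** Mean weight 75 kg; weight CV (CVw) 15-25%; mean delivery 20 Kcal/kg; Kcal/kg CV (CVd) 20-50%; weight independent of Kcal/kg; one mean per patient.

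**4. Variance.** Raw Kcal is weight × Kcal/kg, so CVraw² = CVw² + CVd² + CVw² × CVd².

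| CVw | CVd | CVraw² | CVraw² / CVd² | Interval width, per kg relative to raw |
|---|---|---|---|---|
| 15% | 50% | 0.0225 + 0.25 + 0.0056 = 0.2781 | 1.11 | 0.95 |
| 20% | 30% | 0.04 + 0.09 + 0.0036 = 0.1336 | 1.48 | 0.82 |
| 25% | 20% | 0.0625 + 0.04 + 0.0025 = 0.105 | 2.6 | 0.62 |

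**5. Practical size at 1427 per group** (two-sided 5%, 80% power). Detectable difference = (1.960 + 0.842) × SD × √(2/1427). Central case:

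- Raw: SD = √0.1336 × 1500 = 548 Kcal, giving 58 Kcal/day, or 3.8% of the mean.
- Per kg: SD = 0.30 × 20 = 6, giving 0.63 Kcal/kg, which is 47 Kcal/day at 75 kg, or 3.1% of the mean.

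Power for a difference of 1 Kcal/kg is 95.5% on the raw scale and 99.4% per kg. In the least favourable case (CVw 25%, CVd 50%) it is 64.5% and 76.2%.

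**6. If weight and Kcal/kg are correlated.** To first order, CVraw² = CVw² + CVd² + 2ρ × CVw × CVd. In the central case with ρ = -1/3, this is 0.04 + 0.09 - 0.04 = 0.09 = CVd², so the per-kg scale gains nothing. Weight as a covariate estimates the slope instead of fixing it. To the same order on the log scale, the residual is CVd² × (1 - ρ²) = 0.09 × 0.889 = 0.08, so a small gain remains.

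**7. What the companion endpoints show.** Both are relative to the patient's own prescription or target. Two patients at 100%, one prescribed 20 and the other 25 Kcal/kg, differ in dose by 25/20 - 1 = 25%. The ratio is written as prescribed over delivered, so it rises as delivery falls and is undefined at zero delivery. Section 7.1.4 names a test for the proportion at target but none for the mean ratio. No threshold says when a target that is a range counts as achieved.

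**The case against.** The strongest reply is that the plan already contains what is needed. Daily target achievement is relative to a weight-based target, is analysed with its own model, and covers both the first-week and later targets. A prescription anywhere in the range is on target by protocol. With 1427 per group, weight is balanced in expectation, so similar mean Kcal already points to similar dosing. The planned model compares changes over time, and a patient random intercept would largely absorb stable weight differences from that trend, especially on a log scale.

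Much of this stands. A reader might infer that calorie intake cannot be read against the target at all, or that the equal-dose check is absent. The documents do not support that: the ratio and target-achievement endpoints both tie delivery to the patient's weight-based prescription. What survives is narrower. The Kcal mean cannot be read that way by itself, and the companions do not show where in the range each arm was dosed. A random intercept also does not remove weight variation from the between-arm difference in level.

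Replacing raw Kcal altogether would be wrong. Comparing calories by route is a stated secondary objective, and a per-kg mean over the whole ventilation period would mix two targets.

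**Conclusion.** The point holds as a modest gain in precision and legibility. Under the assumed CVs, with weight independent of Kcal/kg, variance falls by a factor of about 1.1 to 2.6, central 1.5. In the central case the detectable difference goes from about 58 to 47 Kcal/day. The size rests wholly on assumed CVs and on independence; it shrinks if heavier patients receive fewer Kcal/kg, and in the central case it vanishes for simple per-kg scaling at a correlation of about -0.33. The detectable differences also suppose one complete mean per patient, whereas daily records stop at extubation.

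A reader might go further and call the calorie comparison biased, or say that a mortality difference could not be interpreted. Neither follows. Allocation is randomised, the primary analysis does not use calories, and the primary objective compares strategies. This is a free improvement.

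**What to change.** In sections 4.1.2 and 7.1.4:

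- Add total (enteral plus parenteral) Kcal/kg/day as an analysed variable. Divide by the weight that sets the calorie target, which in obese patients is 30 × height² (height in metres), and state which recorded weight that is.
- Summarise it separately for the first week and afterwards, because the target changes. The synopsis starts the higher target on day 8 and section 4.2.3 a on day 7; the two must be reconciled so that the boundary is fixed.
- Add the same weight as a covariate in the mixed model for raw Kcal.
- Keep the planned by-route Kcal comparison, the ratio and target achievement.

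The cost is plan wording and a derived variable; every input is already collected. Section 7.6 finalises the analysis plan at database lock, so the change can be made before then, and should be made before any comparison by arm is seen.
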